11.11 Safety Analysis

Safety will be summarized over the Safety population unless indicated otherwise.

11.11.1Recommended Phase 2 Dose (RP2D)

The primary endpoint for this study is the determination of RP2D in the 28-day continuous dosing of CX-4945 [1000 mg twice daily] of the phase I treatment-duration-increment part of the study, as following:

- If no DLTs are seen in the 3 patients, the treatment-duration-increment part will be closed and the expansion cohorts will be opened. This will be declared the dose for the RP2D.
- If 1 patient out of 3 experiences a DLT, up to 3 additional patients will be recruited (for a maximum of 6). If there are < 2/6 patients with DLT, this will be declared the dose for the RP2D, Phase I will be closed and two expansion cohorts will be opened.
- If 2 out of 3, or 2 out of 6, patients experience DLT, the previous Phase I oral dosing regimen of 1000 mg BID (total daily dose 2000 mg) for 21 days followed by 7 days of rest will be selected for the expansion cohorts.

The procedures and rules to determine the RP2D are given in Section 9.1 of the protocol and as described above. Because of the small number of patients involved in this endpoint, no summaries will be generated. The determination of the RP2D in the RP2D population (see Section 7) will be described textually.

11.11.2Dose Limiting Toxicity (DLT)

Dose limiting toxicity (DLT) will be defined as any of the following drug related adverse events occurring during Cycle 1 (first 28 days of dosing):

- Grade 3 or 4 non-hematologic toxicity (excluding inadequately managed nausea and vomiting, alopecia or grade 3 fatigue lasting < 7 days),
- Grade 4 myelosuppression ≥ 7 days, febrile neutropenia or ≥ grade 3 thrombocytopenic bleeding,

• Other toxicity of concern to the investigators including toxicities requiring delays ≥ 14 days.

All DLTs will be listed and summarized by cohort (treatment-duration-increment, expansion) and overall for the Safety population.

11.11.3Adverse Events

Adverse event terms will be coded using Medical Dictionary for Regulatory Activities (MedDRA) dictionary. A treatment-emergent AE (TEAE) is defined as an AE that starts or worsen on or after the date of the first dose of study medication. Adverse events that have missing onset dates will be considered to be treatment emergent, unless the stop date is known to be prior to the first administration of the study medication. If the AE onset date is partial, the date will be compared as far as possible with the date of first dose of study medication. Adverse events will be assumed to be treatment-emergent, unless there is clear evidence (through comparison of partial dates) to suggest that the AE started prior to the first dose of study medication. All TEAE swill be mapped to thesaurus terms and graded according to the NCI CTCAE, version 5.0.

All AEs will be listed by subject, detailing the verbatim term given by the investigator, the preferred term (PT), system organ class (SOC), onset date, end date, CTCAE Grade, outcome, relationship to study drug, action taken with study drug, other action taken, seriousness and criteria for seriousness. Serious AEs (SAEs) and TEAEs leading to study discontinuation will also be listed separately.

The following TEAE summaries will be produced by cohort (treatment-duration-increment, expansion) and overall:

- An overall summary of safety will summarize the numbers (and percentages) of patients with the following:
 - Any TEAEs and serious adverse event (SAE)
 - AEs related to study drug
 - SAEs related to study drug
 - AEs of Clinical Interest
 - DLTs
 - Who discontinued study drug due to at least one AE (regardless of causality, and related to each study drug)
 - AEs leading to death
- Separate summaries of TEAEs by SOC and PT, subset as follows:
 - All AEs
 - AEs related to study drug. Related AEs will include AEs with a drug relationship of "Related" recorded on CRF.
 - All SAEs
 - SAEs related to study drug
 - All Grade 3 or above AEs

- Grade 3 or above AEs related to study drug
- All AEs in at least 10% of subjects
- AEs in at least 10% of subjects related to study drug
- All AEs leading to discontinuation of study drug
- All AEs leading to dose interruptions
- All AEs leading to dose modifications
- All AEs leading to death, overall, while on study and during the 3-month followup period
- All AEs by SOC, PT and CTCAE toxicity grade
- All AEs by SOC, PT and action taken with study drug
- All AEs by PT

If a patient has multiple occurrences of an AE, the strongest level of relationship to study drug and the worst toxicity grade a patient experiences for a given AE will be used in these tables. Further, if the toxicity grade is missing, the event will be reported as 'unknown' in the summary tables. Likewise, if causality data is missing, 'unknown' will be reported.

11.11.4Clinical Laboratory Testing

Clinical laboratory values will be reported as complete listings of individual subject data. All laboratory values will be classified as normal, low, or high based on normal ranges supplied by the laboratory. Clinical laboratory values outside of normal range will be listed in a separate by-subject listing.

Absolute values and changes from baseline of clinical laboratory data (hematology, chemistry, and continuous urinalysis parameter) will be summarized descriptively. Changes in out-of-range reference flags from Baseline to post-baseline visits in clinical laboratory data will also be summarized using shift tables.

Vitamin D assessments, pregnancy test results will be presented in separate by-subject listings.

11.11.5Vital Signs

Vital signs including body weight, blood pressure (systolic and diastolic), pulse rate, respiratory rate, and body temperature will be presented in a by-subject listing by visit. Absolute values and change from baseline value will be summarized by treatment group using descriptive statistics.

11.11.6Electrocardiogram (ECG)

ECG data measured at Screening will be presented in a by-subject listing.

11.11.7Physical Examination

Physical examination results will be captured on eCRF but will not be presented in tables or listings.

11.11.8ECOG Performance Status

The Eastern Cooperative Oncology Group (ECOG) status of patients will be listed and summarized using frequency counts and percentages by visit.

12.CHANGES FROM THE PROTOCOL AND PLANNED ANALYSES

This SAP reflects the analysis plan outlined in the study protocol without significant change. Any analysis changes or additional analysis not specified in this SAP will have the status of unblinded and exploratory investigations.

13.HEADINGS

Each page of the analysis will show the sponsor's name, the investigational product, and the protocol number. Report tables will be embedded in the MS Word report document from SAS program output without change. The footer of each table will show the name of the SAS program module which generated it, the names of all data sets providing input data in the program and the date and time the table was generated.

14.ARCHIVING AND RETENTION OF DOCUMENTS

After finalization of the analysis, the following will be archived at IQVIA Biotech and/or with the study sponsor:

- SAP and any amendments
- All SAS code used in the project for statistical analysis, report tables generation, and analysis data set creation
- Tables, listings and figures as included in the clinical study report
- SAS study data tabulation model (SDTM) and analysis datasets

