• Sample analysis (fresh frozen tissue or formalin fixed paraffin embedded): Tumor histology will be reviewed and Hh pathway target gene (*GLI1*) and reference gene expression profiling will also be performed on the tumor tissue sample obtained from patients with locally advanced BCC at baseline and at 8 weeks following CX-4945 treatment in order to evaluate the effect of CX-4945 treatment on the Hh signaling pathway.

h. Early Termination or End of Study Assessments

Patients who discontinue from the study will be asked to return to the clinic within 30 days of the last dose of CX-4945 for a follow-up visit. In patients with locally advanced BCC, biopsy of tumor at the time of progression for submittal for pathology review is strongly encouraged.

i. Follow-up Off Protocol Treatment

All patients will be seen at 4 weeks after completion of protocol therapy. Thereafter, continued follow-up is not required for patients who go off protocol treatment with progressive disease, except to document ongoing toxicities (until resolved to < grade 2) and late toxicities (including second malignancies). For patients who go off protocol treatment with CR, PR, or SD ongoing, follow-up will be required every 3 months until relapse (see Appendix A for investigations to be performed). Death report will be required on all patients unless advised by the Sponsor and due within 2 weeks of knowledge of death (see Section 16.3.1).

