16.2.1. Adverse Event Reporting Period

After informed consent, but prior to initiation of study drug, only SAEs caused by a protocol-mandated intervention will be collected (e.g., SAEs related to invasive procedures such as biopsies, medication washout, or no treatment run-in).

After initiation of study drug, all AEs and SAEs regardless of attribution will be collected until 30 days following the last administration of study treatment or study discontinuation/termination, whichever is later. After this period, investigators should report only SAEs that are felt to be related to prior study treatment (see Section 16.6). Additional guidance is provided for pregnancy events occurring within 6 months after the last dose of CX-4945 in Section 16.1.3.

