16.6. POST-STUDY ADVERSE EVENTS

At the last scheduled visit, the investigator should instruct each patient to report to the investigator any subsequent SAEs that the patient's personal physician believes could be related to prior study treatment.

The investigator should notify the CRO of any death or other SAE occurring at any time after a patient has discontinued or terminated study participation if felt to be related to prior study treatment. The CRO should also be notified if the investigator should become aware of the development of cancer or of a congenital anomaly in a subsequently conceived offspring of a patient that participated in this study (refer to Section 16.1.3). The investigator should report these events following the reporting procedures specified in the Section 16.4. If the CRO or the EDC is no longer available, the investigator should report the event directly to Sponsor Drug Safety via [contact]

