- 1. Dispense, administer, and maintain drug accountability of CX-4945. For women of childbearing potential, the investigator must confirm the patient's negative pregnancy test, the patient's understanding of the teratogenic potential of CX-4945, and the use of two acceptable methods of contraception prior to dispensing CX-4945.

- m. The recording of concomitant medications will begin at the time of informed consent and continues through the end of the study period. Record all concomitant medications administered to the patient within the 14 days preceding Day 1.
- n. The reporting period for adverse events (AEs) will begin at the time of informed consent signed and continues until 30 days after the last dose of CX-4945. During screening (i.e., after informed consent, but prior to initiation of study drug), only SAEs related to protocol-mandated procedures should be reported. At the end of the study period, any patient with an ongoing AE or SAE leading to CX-4945 discontinuation will be followed until the event resolves, the investigator assesses the event as stable, or the patient is lost to follow-up.
- o. The recording of cancer-related medical and surgical procedures begins on Day 1 and continues through the end of the study period.
- p.
- q. At 4 weeks then every 3 months thereafter only to follow abnormal results felt related until resolved to \leq Grade 2.
- r. Patients with a CR or PR should have scans repeated after 4 weeks to confirm response.
- s. Every three months until relapse or progression for patients with CR, PR, SD response.

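### The SAP's TEAE definition has no end date and the protocol gives two different ends for AE collection, so events arising well after the last dose can be tabulated as treatment-emergent

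*SAP*

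**What the plan says.** **SAP 11.11.3** defines the term by its start alone: "A treatment-emergent AE (TEAE) is defined as an AE that starts or worsen on or after the date of the first dose of study medication". The date rules have the same open end: "Adverse events that have missing onset dates will be considered to be treatment emergent", unless the event is known to have stopped before first dose. Partial onset dates are also compared only with first dose. No upper limit appears elsewhere in the SAP, and protocol 15.1 uses the term without defining it.

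**Protocol 16.2.1** collects all AEs "until 30 days following the last administration of study treatment or study discontinuation/termination, whichever is later". It then adds: "After this period, investigators should report only SAEs that are felt to be related to prior study treatment". Section 16.6 sets no time limit on the latter and covers "any death or other SAE occurring at any time after a patient has discontinued or terminated study participation if felt to be related" to study treatment.

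**Appendix A, footnote n** says that AE reporting "continues until 30 days after the last dose of CX-4945", with no alternative tied to study discontinuation. The flowchart nevertheless marks AE evaluation, tagged with this footnote, in the 3-month follow-up column.

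**Protocol 12.1(i)** covers patients who leave treatment with an ongoing CR, PR or SD: "follow-up will be required every 3 months until relapse".

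**How the SAP uses the term.** The AE tables in 11.11.3 are introduced as TEAE summaries, by cohort and overall. One of them covers fatal AEs, including those in the 3-month follow-up. For repeated occurrences of an AE, the patient's worst grade and strongest relationship are used.

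**The concern.** An open-ended definition does little harm if data collection stops soon after the last dose, because collection then acts as the cap. Here the protocol states two different stopping points, and one of them can fall long after exposure ends. A table headed treatment-emergent could then mix on-drug events with events that began months after the drug was stopped.

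Because the worst grade across all occurrences is reported, a late recurrence can raise the grade attributed to the treatment period even if no new patient is added to the row. Sites that follow different sections of the protocol would also collect different data. In a trial this small, one patient visibly moves a percentage.

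**Working it through.** The documents give no figure to reproduce, so the check is a comparison of windows followed by simple proportions.

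**1. The windows.** Let L be the day of last dose and S the day of study discontinuation. Footnote n closes at L + 30. The wording of 16.2.1 can be read in two ways: (A) max(L, S) + 30, or (B) max(L + 30, S). The SAP definition never closes. The values of L and S below are assumptions, since the documents give no actual times.

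| L | S | Footnote n | 16.2.1 (A) | 16.2.1 (B) | Gap A / B (days) |
|---|---|---|---|---|---|
| 56 | 56 | 86 | 86 | 86 | 0 / 0 |
| 56 | 148 | 86 | 178 | 148 | 92 / 62 |
| 112 | 274 | 142 | 304 | 274 | 162 / 132 |
| 56 | 274 | 86 | 304 | 274 | 218 / 188 |

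The windows agree when the patient leaves the study at last dose. They separate when the patient stays on study off drug, and both readings of 16.2.1 then exceed footnote n.

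**2. Who can be affected.** Treatment runs until progression, intolerable toxicity or withdrawal (protocol 9.1, 11.3). Patients who progress need no continued follow-up except for ongoing and late toxicities (12.1(i)), and withdrawal of consent ends follow-up (12.1). The exposed group is therefore mainly patients who stop drug in CR, PR or SD and remain in 3-monthly follow-up. The documents give no count of them.

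**3. Is such a patient still on study?** Protocol 9.4 runs the study period to documented progression, and the opening of 12.1 follows patients to progression, death or withdrawal of consent. On that basis S falls late. Sections 12.1(h) and 12.4 ask patients who discontinue from the study to return within 30 days of last dose, which can be read as placing S near L. The text does not settle it.

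**4. What holds on either reading.** A related SAE is reportable at any time (16.2.1, 16.6) and meets the SAP definition whatever its distance from last dose.

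**5. Weight of one patient.** SAP section 6 says that 2 mBCC patients were enrolled in the expansion. Assume the planned 10 locally advanced patients, the planned 3-6 run-in patients and no replacements:

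- Overall: n = 3 + 10 + 2 = 15 to 6 + 10 + 2 = 18. 1/15 = 6.7% and 1/18 = 5.6%.
- Expansion: n = 10 + 2 = 12. 1/12 = 8.3%. A second patient gives 2/12 = 16.7%, so one late event can carry a term into the SAP's table of AEs in at least 10% of subjects.
- Run-in: 1/6 = 16.7% and 1/3 = 33.3%.

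These are ceilings. A late event adds a patient to a row only if that patient had no earlier event with the same term. Otherwise it changes the table only by raising the grade or relationship.

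**The case against.** The strongest reply is that the long window rests on one reading. If study discontinuation means the visit within 30 days of last dose, the two protocol windows nearly coincide and only late related SAEs remain. That is a fair reading, and it is why the effect is stated conditionally. It does not remove the difference in wording between 16.2.1 and footnote n, or give the SAP an end date.

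It is also true that the trial is descriptive with no formal hypothesis testing (SAP 10.5), that related events are tabulated separately, and that every AE is listed with its onset date, so late events can be found. These points limit the consequence. The main tables would still carry a misleading label.

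A reader might infer more than the documents support:

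- **That Appendix A itself schedules collection of new AEs at the 3-monthly visits.** The cell carries footnote n, which ends reporting at 30 days and then follows only ongoing events that led to discontinuation. The cell fits follow-up of known events and is not independent evidence of late collection.
- **That TEAE rates are distorted by response status or by later anti-cancer therapy.** No table compares progressors with non-progressors, the number of patients followed off drug is unknown, and this follow-up ends at relapse. The SAP's censoring rules allow for new therapy before progression, but nothing shows that it occurred.
- **That the denominator is the planned 26.** The 2 mBCC patients in SAP section 6 rule that out on planned numbers.
- **That the RP2D is in doubt.** DLTs are confined to Cycle 1 (SAP 11.11.2).

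**Conclusion.** The point holds as a defect of definition with a limited reach. The SAP sets no end to the TEAE period, and the protocol's two statements of when AE collection ends conflict for any patient who stays on study after stopping drug. Followed as written, the rule counts related SAEs at any time as treatment-emergent. If follow-up patients count as on study, it also counts other off-drug events and lets them overwrite an on-drug worst grade or relationship.

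Per affected patient, the most it can add to a row is about 6-7 percentage points overall, about 8 in the expansion cohort and 17-33 in the run-in cohort. This assumes the planned run-in and locally advanced numbers plus the 2 mBCC patients. The total effect cannot be stated, because the number of such patients is not given. This is a minor point that is worth correcting because correction is cheap.

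**What to change.** 1. In SAP 11.11.3, define a TEAE as an AE with onset or worsening from first dose through 30 days after last dose, and apply the same upper limit in the rules for missing and partial dates where the recorded dates allow.
2. Summarise later events in a separate post-treatment table and listing. Include late related SAEs in that table, so that they are not only listed, and keep there the already planned summary of fatal AEs in the 3-month follow-up.
3. Reconcile protocol 16.2.1 with Appendix A footnote n and the 3-month follow-up cell, and say whether a patient in off-treatment follow-up is still on study. SAP section 6 already reports early termination. If collection is finished, state in the study report which window sites used.

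The cost is a sentence or two in the SAP, one date comparison in programming, one extra table and a protocol clarification or study-report statement. No new data are needed. The downside is that late events leave the main TEAE tables, so a reader must consult the post-treatment table to see them.

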7.2. BACKGROUND ON THE MOLECULE

7.3. RATIONALE FOR DOING THIS STUDY

7.4. DOSING REGIMEN AND STARTING DOSE

CX-4945 will be administered twice a day on a continuous basis. Each cycle will be 28 days (4 weeks) in duration and the first cycle will be used as the DLT observation period.

The starting dose will be 1000 mg BID (2000 mg total daily dose). This starting dose is based on three completed Phase I studies where patients were administered CX-4945 following a twice-daily (BID) or four-times-daily (QID) dosing regimen for 21 days followed by 7 days of rest. A total of 12 patients were treated at the 1000 mg bid dose level. Grade 3 or greater hypokalemia and hyponatremia associated to CX-4945 were reported but no drug-related severe diarrhea was noted. At the 1000 mg bid dose level, 1 out of 12 patients had DLT, grade 4 hypokalemia.

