16.3. PROCEDURES FOR RECORDING ADVERSE EVENTS

16.3.1. Recording Adverse Events on the eCRF

Investigators should use correct medical terminology/concepts when recording AEs or SAEs on the eCRF and should avoid colloquialisms and abbreviations. Only one medical concept should be recorded in the event field on the AE/SAE eCRF page.

A. Diagnosis versus Signs and Symptoms

If known, a diagnosis should be recorded on the eCRF rather than individual signs and symptoms (e.g., record only liver failure or hepatitis rather than jaundice, asterixis, and elevated transaminases). However, if a constellation of signs and/or symptoms cannot be medically characterized as a single diagnosis or syndrome at the time of reporting, each individual event should be recorded as an AE or SAE on the eCRF. If a diagnosis is subsequently established, it should be reported as follow-up information.

B. Adverse Events Occurring Secondary to Other Events

In general, AEs occurring secondary to other events (e.g., cascade events or clinical sequelae) should be identified by their primary cause. For example, if severe diarrhea is known to have resulted in dehydration, it is sufficient to record only diarrhea as an AE or SAE on the eCRF.

However, medically significant AEs occurring secondary to an initiating event that are separated in time should be recorded as independent events on the eCRF. For example, if a severe gastrointestinal hemorrhage leads to renal failure, both events should be recorded separately on the eCRF.

C. Persistent or Recurrent Adverse Events

A persistent AE is one that extends continuously, without resolution between patient evaluation timepoints. Such events should only be recorded once on the eCRF unless their severity increases. If a persistent AE becomes more severe, it should be recorded again on an AE/SAE eCRF.

A recurrent AE is one that occurs and resolves between patient evaluation timepoints and subsequently recurs. All recurrent AEs should be recorded on an AE/SAE eCRF.

D. Abnormal Laboratory Values

Only clinically significant laboratory abnormalities that require active management will be recorded as AEs or SAEs on the eCRF (e.g., abnormalities that require study drug dose modification, discontinuation of study treatment, more frequent follow-up assessments, further diagnostic investigation, etc.).

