9. INTERIM ANALYSIS

No interim analysis is planned for this study.

10.DATA CONVENTIONS FOR ANALYSIS

10.1General Statistical Principles

All statistical processing will be performed using SAS® unless otherwise stated. Any statistical tests will be two-tailed at significance level of 0.05 unless otherwise specified.

All observed and derived variables (e.g., change from baseline, percentage change from baseline, and response status) used in the summaries of analyses will be presented in by-subject listings. Unless otherwise noted, the data will be sorted first by treatment assignment, then by subject number and then by date within subject number.

Efficacy and safety results will be summarized descriptively. Categorical parameters will be summarized by the number and percentage of subjects in each category. Denominators for percentages will be appropriate to the purpose of the analysis. Percentages will typically be presented to one decimal (Note: 0% and 100% will be in integer format). Continuous parameters will be summarized as number of subjects, mean, standard deviation (SD), median, minimum, and maximum.

10.2Study Day

Day 1 is defined as the date of first study drug administration. Study day is calculated relative to the date of Day 1. For subjects who did not have a recorded date of first study drug administration, study day will not be calculated.

10.3Baseline and Change from Baseline

Baseline is defined as the last non-missing assessment prior to the first administration of study drug. Change from baseline is defined as post-baseline value minus baseline value unless otherwise specified. Percent change from baseline is (Change from baseline / Baseline) * 100%.

10.4Analysis Visit Window

Results will be summarized according to the visit as recorded in the eCRF. No visit windows will be applied.

10.5Multiple Comparisons

Not applicable. There will be no formal hypothesis testing.

11.STATISTICAL EVALUATION

11.1Subject Disposition

The number and percentage of subjects screened, enrolled, included in key analysis populations, completing the study, and withdrawing from the study (together with the reasons for withdrawal) will be summarized using frequencies and percentages, overall and by cohort (treatment-duration-increment, expansion).

A by-subject listing will show all subjects enrolled and their disposition.

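### Laboratory severity is not tabulated by CTCAE grade independently of adverse-event reporting: the shift tables use low/normal/high flags and no worst post-baseline summary is planned

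*SAP*

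**What the plan says.** SAP 11.11.4 sets the laboratory classification: "All laboratory values will be classified as normal, low, or high based on normal ranges supplied by the laboratory". The shift tables follow from it: "Changes in out-of-range reference flags from Baseline to post-baseline visits in clinical laboratory data will also be summarized using shift tables".

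The same section plans three further outputs:
- Numeric summaries: "Absolute values and changes from baseline of clinical laboratory data (hematology, chemistry, and continuous urinalysis parameter) will be summarized descriptively". SAP 10.1 fixes the statistics: "Continuous parameters will be summarized as number of subjects, mean, standard deviation (SD), median, minimum, and maximum".
- Full listings: "Clinical laboratory values will be reported as complete listings of individual subject data".
- An abnormal-value listing: "Clinical laboratory values outside of normal range will be listed in a separate by-subject listing".

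CTCAE grading in SAP 11.11.3 applies to adverse events, which are tabulated by grade and as Grade 3 or above. Whether a laboratory change becomes an adverse event is settled by Protocol 16.3.1 D: "Only clinically significant laboratory abnormalities that require active management will be recorded as AEs or SAEs on the eCRF".

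On the drug's history, Protocol 7.4 says: "Grade 3 or greater hypokalemia and hyponatremia associated to CX-4945 were reported". It adds that the one DLT among 12 patients at 1000 mg twice daily was Grade 4 hypokalemia. Those patients were dosed for 21 days with 7 days of rest. This trial tests 28 continuous days.

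**The concern.** A three-level flag records on which side of the normal range a value lies, not how far outside it. Severity is the open question for potassium and sodium here. The eligibility criteria set no numeric limit for either test, so a patient can enter with a low value. In the shift table, such a patient looks the same after a slight further fall as after a fall to Grade 4.

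The adverse-event tables do carry grades, but they hold only what the investigator judged recordable. Safety and tolerability is a secondary objective, and Protocol 9.2 counts clinical laboratory results within the secondary safety outcome. A reader of the study report will want to know how many patients reached Grade 3-4 hypokalemia or hyponatremia on continuous dosing. No planned table answers that from the laboratory data themselves.

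**Working it through.** The plan gives no figure on this point to reproduce. The check has three parts: what the flag table merges, where a severe value would appear, and how large the question is.

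**1. What the flag table merges.** Assumption: Grade 0 is within range and Grades 1 to 4 are below the lower limit (the documents do not print the CTCAE cut-offs). Take pairs of baseline grade and worst later grade from 0 to 4, with the later grade higher.
- All worsening pairs: 5 × 4 / 2 = 10.
- Starting from Grade 0: 4 pairs (to 1, 2, 3 or 4), all shown as *normal to low*. Two of them end at Grade 3 or 4.
- Starting from Grade 1 or above: 4 × 3 / 2 = 6 pairs (1 to 2, 3 or 4; 2 to 3 or 4; 3 to 4), all shown as *low to low*. Five of them end at Grade 3 or 4.
- *Low to low* covers 4 × 4 = 16 grade pairs in all: 6 worsening, 4 unchanged and 6 improving. It cannot tell these apart.

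A grade shift table would separate all ten worsenings. The flag table puts them in two cells.

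**2. Where a severe value would appear.**

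| Planned output | What it shows of a Grade 3-4 fall |
|---|---|
| Flag shift table | Low, with no degree |
| Numeric summary by visit | May set the minimum; gives no number of patients |
| Full and out-of-range listings | The value itself; no grade and no count |
| Graded adverse-event tables | Counted by grade, if recorded as an adverse event |

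The last row depends on the recording rules. For a drug-related Grade 3 or 4 toxicity, Protocol 11.6 calls for a hold and addresses dose reduction. Protocol 16.3.1 D counts dose modification, more frequent follow-up and further investigation as active management, so such a value should be recorded and graded. Four routes can still leave a value out of the graded count:
- *Judged not clinically significant.* Protocol 16.3.1 D then does not call for recording. The exceptions to intolerable toxicity in Protocol 9.4 show that this judgement is foreseen for routine chemistry findings.
- *Judged unrelated.* Under Protocol 16.2.2 another sufficient explanation makes causality negative. The Protocol 11.6 table covers related toxicity only, so its trigger is absent. The value is recorded only if it is actively managed for another reason.
- *Recorded under its cause.* Protocol 16.3.1 B generally names secondary events by their primary cause, with diarrhea leading to dehydration as its example. Section D records only the diagnosis when the abnormality is a sign of one. Low potassium put down to diarrhea could therefore be entered as diarrhea, at the grade of the diarrhea. Medically significant secondary events separated in time must be recorded separately.
- *Nadir between visits.* This affects the laboratory tables. Protocol Appendix A schedules chemistry every 4 weeks. SAP 10.4 summarizes by eCRF visit without windows, and no worst value is defined. A nadir at an unscheduled visit may appear only in listings.

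**3. Scale.** The earlier DLT rate is 1/12 = 8.3% (exact 95% interval 0.2% to 38.5%). If such events occur at that rate, the chance of at least one in n patients is 1 − (11/12)^n: 73% for n = 15, 79% for n = 18, and 90% for n = 26. The 26 is the planned total in Protocol 18. The 15 to 18 is an assumption: 3-6 run-in patients, 10 locally advanced, and the 2 metastatic patients that SAP 6 reports. Actual locally advanced enrolment is not stated. One patient is 1/18 = 5.6% to 1/15 = 6.7% of the treated population, or 1/26 = 3.8% at the planned total. These figures show what one patient weighs. They do not estimate how many would be missed.

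**The case against.** A reader might infer that the flag shift is the only view of laboratory severity, and that a known toxicity of the drug can therefore go unseen. The documents do not support that. A patient who is low at baseline and falls further has a negative change from baseline, may set the visit minimum, and appears in both listings. With at most about 26 patients, those listings can be read one by one.

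A reader might also infer that Grade 3-4 incidence cannot be obtained, or that severe values escape grading. That too goes too far. A drug-related Grade 3-4 fall handled under Protocol 11.6 meets the recording rule in 16.3.1 D and is recorded again if its severity changes. Under SAP 11.11.3 it is treatment-emergent if it starts or worsens on study drug, and it is tabulated at the patient's worst grade. The adverse-event route is built for the headline case.

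Nor does the point reach the RP2D decision. DLTs are drug-related adverse events by definition, and a laboratory table would not alter that rule. Finally, Protocol 15.1 promises only summaries of laboratory results, which the SAP supplies, so nothing is contradicted.

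All of this stands. What remains is that a listing gives no incidence, a minimum is one patient's value, and the graded tables reflect judgements on significance, relatedness and primary cause.

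**Conclusion.** The point holds as a gap in tabulation. SAP 11.11.4 plans no CTCAE-graded and no worst post-baseline laboratory summary, so the number of patients reaching Grade 3-4 is not tabulated independently of investigator adverse-event reporting. Within the shift tables all ten low-side worsenings collapse into two cells, given the assumption that every grade from 1 to 4 lies outside the normal range.

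The number of patients affected cannot be derived from the documents. It may be none, because most drug-related Grade 3-4 values should reach the graded tables. The values at risk are those judged not clinically significant, those judged unrelated and not otherwise managed, and those recorded only under their cause. The primary endpoint is untouched. The change is still worth making, because this is the toxicity named in the protocol's own dose rationale and the trial lengthens the dosing period.

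**What to change.** In SAP 11.11.4, derive CTCAE v5.0 grades for tests whose grade can be set from the numeric value: at least potassium and sodium, plus the other gradable hematology and chemistry tests already collected. Tabulate baseline grade against worst post-baseline grade in the Safety population, by cohort and overall, using scheduled and unscheduled values. Grade the low and high directions separately for tests that can move either way. State the convention where the value alone does not settle the grade.

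Place this in the SAP before the analysis, because SAP 12 gives later additions exploratory status only.

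The cost is a little programming on data already held, with no site work. The drawback is that value-derived grades may differ from investigator grades, so show both and explain the difference in a footnote.
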